### **12.2 Sample Size Estimation**

Enrollment is planned for 550 subjects overall (275 subjects per treatment group). The primary analysis for immunogenicity will be an equivalence test using the 2 one-sided tests (TOST) approach with  $\alpha=0.05$ . This sample size was chosen to achieve over 80% power on the equivalence test of proportion of subjects under the margins dependent on the observed treatment-induced AIA rate. For example, a sample size of 550 will provide approximately 85% power on the equivalence test of proportion of subjects with treatment-induced AIA using an event rate of 30% and a margin of 12% (Table 4). The treatment-induced AIA is defined as newly confirmed positive AIA development or important (at least a 4-fold) increase in AIA titers, after baseline and up to visit Week 26. For this sample size of 550, no dropouts are considered in the calculation. Subjects will be encouraged to come back for assessments even if they have discontinued treatment early.

The similarity margin, based on the actual observed event rate for the intended reference product, will be used for final analysis after database lock as summarized in Table 4. Linear interpolation will be used for values between AIA rates in the table.

**Table 4: Similarity Margins for Actual Observed Event Rate of Proposed Biosimilar to Insulin Glargine for Various Immunogenicity Event Rates**

Treatment-induced AIA Rate for the Reference Product	Margin	Power
10%	7.9%	83%
15%	9.3%	83%
20%	10.5%	84%
25%	11.3%	84%
30%	12.0%	85%
35%	12.5%	85%
40%	12.8%	85%
45%	13.0%	85%
50%	13.1%	85%
55%	13.0%	85%
60%	12.8%	85%
65%	12.5%	85%
70%	12.0%	85%
75%	11.3%	84%
80%	10.5%	84%
85%	9.3%	83%
90%	7.9%	83%

AIA = anti-insulin antibodies.

Sample size calculations were performed using EAST Version 6.4.

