**Table 5: Imputation Rules for Missing Data in the Primary Immunogenicity Analysis**

	Baseline a	Visit Week 12	Visit Week 26	Result/Imputation Rule
1.	x	x	x	No imputation.
2.	x	x	o	Subject will be counted as developing a treatment-induced AIA, impute visit Week 26 as positive result
3.	x	o	x	Subject will be counted as developing a treatment-induced AIA, impute visit Week 12 as positive result
4.	x	o	o	Subject will be counted as developing a treatment-induced AIA, impute visit Week 12 and visit Week 26 as positive result
5.	o	x	x	Subject will be counted as developing a treatment-induced AIA if visit Week 12, visit Week 26, or unscheduled assays up to visit Week 26 indicate positive result; otherwise, subject will be counted as not developing a treatment-induced AIA (all assays up to visit Week 26 are negative).
6.	o	x	o	Subject will be counted as developing a treatment-induced AIA, impute visit Week 26 as positive result
7.	o	o	x	Subject will be counted as developing a treatment-induced AIA, impute visit Week 12 as positive result
8.	o	o	o	Subject will be counted as developing a treatment-induced AIA, impute visit Week 12 and visit Week 26 as positive result

AIA = anti-insulin antibodies; o = AIA data missing, x = AIA data not missing.

a No imputation will be performed for missing baseline values.

Additional sensitivity analyses on the imputation, which explore the limitation(s) of the data or assumption(s) of the primary analysis being evaluated in each sensitivity analysis and how the analysis addresses each, will also be discussed in the SAP.

Missing data will be imputed for the HbA1c analysis. The robustness of the imputation will be explored via sensitivity analyses using multiple imputation and including a tipping point analysis. Full details of the multiple imputation procedure will be presented in the SAP.

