11.6.1 Primary Endpoint

11.6.1.1 Incidence of Treatment-Induced Anti-Insulin Antibodies

Incidence of treatment-induced AIA is defined as subjects develop newly confirmed positive AIA or have important (4-fold) increase in AIA titer up to visit Week 26. The objective of the primary immunogenicity analysis will be to evaluate equivalence of Gan & Lee Insulin Glargine Injection to Lantus® by comparing the limits of the 90% confidence interval (CI) of difference in proportion of treatment-induced AIA development to the specified margins (-margin, +margin) where the margin is dependent on the unadjusted treatment-induced AIA rate in Lantus® and is defined in Section 5.1, Table 3.

The estimand of interest for the primary immunogenicity analysis is the difference in treatment-induced AIA rates regardless if all subjects tolerate or adhere to study treatment or receive other insulin treatments. Intercurrent events will be handled according to the treatment policy strategy. Treatment Policy strategy is defined as the strategy that considers "The occurrence of the intercurrent event is irrelevant: the value for the variable of interest is used regardless of whether or not the intercurrent event occurs" (See ICH E9 R1 addendum). All AIA data collected, scheduled and unscheduled, will be considered for the analysis, even if collected after the occurrence of intercurrent events of (1) discontinuing study treatment, (2) returning to initial treatment and/or (3) initiating a new treatment.

Any treatment-induced AIA after baseline and up to visit Week 26 will have the subject count as treatment-induced AIA for the primary endpoint. For subjects who have no AIA measurement at scheduled visit Week 12 or 26, AIA measurements from returned visits that fall within the allowed visit window (visit Week 12 ± 1 week or visit Week 26 ± 4 weeks, defined in Section 7.1) will be assigned to the respective time point.

Missing data will be handled as described in Section 11.6.1.2. The SS will be used for the primary analysis.

The number and percentage of subjects in each treatment group who develop treatment-induced AIA as defined in Section 7.2 after baseline and up to visit Week 26 (upper limit of the visit window) will be evaluated using a logistic regression model in proportions along with the corresponding 90% CI.

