Equivalence in difference in proportion δ between Gan & Lee Insulin Glargine Injection (π_1) and Lantus® (π_2) will be tested by comparing the limits of the 90% CI for treatment-induced AIA development with the following null hypothesis:

$$H_0: (\pi_1 - \pi_2) \leq -\delta_0 \text{ or } (\pi_1 - \pi_2) \geq \delta_0$$

Against the alternative hypothesis of:

$$H_1: -\delta_0 < (\pi_1 - \pi_2) < \delta_0$$

where δ_0 is the margin dependent on the observed unadjusted treatment-induced AIA rate in Lantus® (π_2) and is defined in Section 5.1, Table 3.

To evaluate equivalence of Gan & Lee Insulin Glargine Injection to Lantus® the calculated 90% CI has to be entirely contained with the interval $(-\delta_0, \delta_0)$.

A sample SAS code fragment is provided below for reference:

```
proc logistic data=<data>;
    class trt / param=ref ref='Lantus';
    model response=trt;
run;
```

The Fisher scoring algorithm will be used for maximum likelihood estimation of the regression parameters. The difference in proportions along with the corresponding 90% CI in the SS using a logistic regression model will be calculated. The delta method will be used to calculate the standard error for the difference and the associated confidence interval (Ge M, Durham LK, Meyer RD 2011 (4)).

Subjects were randomly assigned to treatment using variable block size (See Section 5.2). Blocking should be taken into account when the intra-block correlation is non-zero (Matts and Lachin 1988 (5)). An intra-block correlation of zero can be safely ignored in the analysis (Efird 2011 (6)). Subjects are generally anticipated to remain within sites so the intra-block correlation within investigative site can be assumed to be zero and therefore no adjustment for block is planned.

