11.6.1.2 Methods for Handling Dropouts and Missing Data

Utilizing a "Treatment Policy" strategy, missing data (after using data collected during or after treatment, and assigning data to the appropriate scheduled visit as described above) for the primary endpoint will be imputed as per Table 4. Sites have been trained in the importance of collecting baseline AIA samples. In the rare and unlikely event a site does not collect a baseline AIA sample, imputation rule for missing baseline assessment is included in the table. Unscheduled assessments (e.g. EOT documented at visit Week 26 outside the visit windows for discontinued subjects) up to visit Week 26 will be considered in the overall result but will not be imputed.

Table 4: Imputation Rules for Missing Data in Primary Immunogenicity Analysis

Category	Sample Availability	Imputation	Likely Scenarios
1	All three AIA samples collected and analyzed	
 No imputation 	
 Subjects complete the study. Dropout subjects provide the required AIA samples within the defined visit window.
2	At least one AIA sample missing at Week 12 or Week 26 regardless of baseline sample availability	
 Subject will be counted as 'developing a treatment-induced AIA'. 	
 Dropout subjects who are unable to provide AIA samples in respective visit window. AIA sample missing due to protocol deviations.

Category	Sample Availability	Imputation	Likely Scenarios
3	Baseline sample missing, but both Week 12 and Week 26 samples are collected and analyzed	
 Subject will be counted as 'developing a treatment-induced AIA' if any of Week 12 or Week 26 results are positive. Subject will be counted as 'NOT developing a treatment-induced AIA' if both Week 12 and Week 26 results are negative. 	
 Baseline AIA sample missing due to protocol deviations.

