11.6.1.3 Sensitivity Analyses

Inherent in the primary endpoint analysis described above are several implicit assumptions that can possibly affect the generalizability of immunogenicity. There are four assumptions that are important to mention. The primary analysis assumes that the impact on the immunogenicity conclusion of early discontinuations, important protocol deviations, less than full treatment duration and patterned missing data is negligible. Although the scientific rationale to make these assumptions is reasonable, sensitivity analyses for the primary endpoint of immunogenicity to assess the impact of these effects are planned, as follows.

- 1) **Composite Strategy:** Subjects in the SS with the intercurrent event of discontinuing treatment will be considered as having a treatment-induced AIA. Results of assessment after the end of treatment are excluded from the analysis. The imputation approach as described in Table 4 will be used for missing data. This sensitivity analysis will examine the assumption that results were not impacted by the discontinuation of treatment (as these will be imputed as positive immune response).
- 2) **Per Protocol Analysis Set (PPS):** Subjects with any important protocol deviations (as defined in Section 11.3) will be excluded from the analysis. For subjects in the PPS, the imputation approach as described in Table 4 for primary analysis will be followed. In the primary analysis, subjects with important protocol deviations could falsely draw the estimated treatment difference closer. Exclusion of these subjects in this sensitivity analysis will help assess the magnitude, if any, of this effect.
- 3) **SS - Completers:** This analysis will not use any imputation of missing data. Only subjects with valid baseline and visit Week 12 and Week 26 assessments conducted within the required visit window (visit Week 12 \pm 1 week and visit Week 26 \pm 4 weeks, respectively) and who had treatment until visit Week 26 will be used for the analysis. Subjects with less than a full treatment duration could

underestimate the proportion of subjects reporting positive immune response. By including only completers, as in this sensitivity analysis, this estimated treatment difference is determined only by subjects whose treatment duration was full.

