- 4) Per Protocol Analysis Set 2 (PPS2) - Subjects with any immunogenicity-interfering important protocol deviations (IIPD; as defined in Section 11.3) will be excluded from the analysis. For the subjects in the PPS2, the imputation approach as described in Table 4 for primary analysis will be followed. In the primary analysis, subjects with immunogenicity-interfering important protocol deviations could falsely draw the estimated treatment difference closer. Exclusion of these subjects in this sensitivity analysis will help assess the magnitude, if any, of this effect.
- 5) ERIPD Interaction Analysis for immunogenicity – To assess the impact of eligibility related important protocol deviations on the treatment effect for immunogenicity, this analysis will be carried out using an extended model of the main analysis, by including ERIPD (yes/no) and treatment by ERIPD interaction as factors. The interaction parameter estimate, 90% CI and p-value will be presented with number and percentage of subjects in each ERIPD category under each treatment arm.

All these sensitivity analyses will be conducted as described for the primary analysis, using the same margins from the primary analysis.

Additional analyses examining the development of treatment-induced AIA at Week 26 in the following subgroups using the SS with imputation as described in Table 4 for primary analysis will be presented in a forest plot:

- Gender (Male versus Female)
- Age (< 65, versus ≥ 65 years old)
- Race (white versus non-white)
- BMI (Obese versus Non-obese)
- Menopausal Status (Pre- versus post-)
- Dosing Regimen (Twice daily (BID) Dosing at least once versus daily (QD) Dosing)
- Previous Exposure to Lantus® (No previous exposure versus previous exposure (within 6 months prior to study initiation))

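### Counting missing AIA samples as events in both arms favours equivalence when missingness is similar; the rate that sets the margin is unclear and the promised worst-case analysis is not listed

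*SAP*

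**What the plan says.** **Missing samples.** SAP 11.6.1.2, Table 4, category 2 covers any subject with "At least one AIA sample missing at Week 12 or Week 26 regardless of baseline sample availability" and counts that subject as an event, whatever the arm. Protocol Table 5 agrees for every pattern with a missing post-baseline sample. The row with only Week 26 missing reads "Subject will be counted as developing a treatment-induced AIA, impute visit Week 26 as positive result". Under SAP 11.6.1.1, samples taken after discontinuation are used and return-visit samples inside the windows are assigned to the visit, so the rule applies to what is still missing after that.

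**Margin.** Protocol 12.2 and SAP 5.1 take the margin from SAP Table 3 (Protocol Table 4), "based on the actual observed event rate for the intended reference product". SAP 11.6.1.1 says the "margin is dependent on the unadjusted treatment-induced AIA rate in Lantus" and, under the hypotheses, "margin dependent on the observed unadjusted treatment-induced AIA rate in Lantus", labelled π_2, the symbol also used for the tested Lantus proportion.

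**Sensitivity analyses.** Protocol 12.6.1 promises "Additional sensitivity analyses on the imputation, which explore the limitation(s) of the data or assumption(s) of the primary analysis". Protocol 12.7.1 names worst-case imputation and a composite strategy. SAP 11.6.1.3 lists five analyses: Composite, PPS, SS-Completers, PPS2 and an ERIPD interaction, all "using the same margins from the primary analysis". The same section says that the primary analysis assumes the impact of early discontinuations, important deviations, "less than full treatment duration and patterned missing data is negligible".

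**The concern.** In a comparison meant to show a difference, treating missing as an adverse outcome can be called cautious. In an equivalence test of a difference in proportions, giving the same outcome to missing subjects in both arms pulls the arms together when missingness is similar. SAP 11.6.1.3 recognises the danger of subjects falsely drawing the difference closer, but applies it only to protocol deviations and not to its own imputation.

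Three matters combine. The primary test can exceed its 5% error. The rate that selects the margin can be read with or without imputed positives, so two statisticians could reach different primary conclusions from the same data. And no listed analysis tests the imputation in opposite directions in the two arms within the treatment-policy estimand. SAP 5.1 makes this relevant: it allows for no dropouts and reports more early discontinuation than expected.

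**Working it through.** **Inputs.** 275 subjects per arm, a 90% CI that must lie inside ±margin, true difference zero for power (SAP 5.1, 11.6.1.1); margins from SAP Table 3, linearly interpolated. The model contains treatment only, so its delta-method interval equals the unpooled Wald interval. *Assumptions:* equal missingness of 5/10/20% and Lantus rates of 20, 30 and 60%. The documents give neither the missing-sample rate nor the Lantus rate.

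**1. The plan's own figure.** Power = 2Φ(m/SE − 1.645) − 1, with SE = √(2·0.30·0.70/275) = 0.0391 and m = 0.12. The result is 84.6% (84.9% by exact enumeration), against a stated 85%. It reproduces.

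**2. Shrinkage.** Only a missing subject without a true event changes status, so the apparent rate is p + (1−p)f. The difference becomes (p1 − p2)(1−f). Missingness among true events does not matter.

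**3. Worked case.** Lantus 30%, test 42% (on the upper margin), f = 10%.
- Lantus: 0.30 + 0.70·0.10 = 37.0%. Test: 0.42 + 0.58·0.10 = 47.8%.
- The difference falls from 12.0 to 10.8 points; SE = √(0.478·0.522/275 + 0.370·0.630/275) = 0.0419.
- Margin kept at 12.0%: chance of passing ≈ Φ((0.120 − 0.108)/0.0419 − 1.645) = Φ(−1.36) = 8.7%; exact 8.5%.
- Margin read at 37.0%: 12.5 + (2/5)·0.3 = 12.62%, so the margin widens as well; exact 12.0%.

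**4. Error at Lantus 30%, upper / lower margin.** Exact enumeration; the complete-subject margin additionally averages over the number missing.

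| Missing | Margin fixed at true rate | Imputed positives in margin rate | Margin from complete Lantus subjects |
|---|---|---|---|
| 0% | 4.9 / 5.0% | 5.8 / 3.8% | 5.8 / 3.8% |
| 5% | 6.8 / 6.9% | 8.3 / 6.8% | 7.5 / about 5.5% |
| 10% | 8.5 / 9.1% | 12.0 / 11.0% | 9.6 / 7.5% |
| 20% | 13.4 / 14.6% | 19.8 / 19.2% | 14.9 / 12.7% |

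The 0% row shows that the data-driven margin alone moves the errors to 5.8/3.8%; that part is not due to Table 4. With the margin fixed at the true rate, the error reaches 10% at about 13% missing for the lower margin and 14–15% for the upper (Lantus 20% or 30%).

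**5. Other Lantus rates.** At 20% with the complete-subject margin, upper errors are 7.8/9.6/13.7% and lower errors 4.6/6.6/11.0%, so at 5% missing only the upper margin is exceeded. At 60%, upper errors at 10/20% missing are 7.5/11.3% with imputed positives in the margin rate and 8.8/15.4% with the complete-subject margin.

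**6. Unequal missingness** (Lantus 30%, margin fixed at true rate). Test 10% against Lantus 15% missing: upper error 28.7%. Test 15% against Lantus 10%: upper 1.9%, lower 36.9%.

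**7. Power at true equality.** With imputed positives in the margin rate it stays near 84%, so the problem would not show as a failed trial. With the complete-subject margin, at 5/10/20% missing, it is 78/72/63% (Lantus 20%), about 82/79/76% (Lantus 30%) and about 85/87/88% (Lantus 60%).

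**8. Listed sensitivity analyses.** Composite, PPS and PPS2 keep Table 4. Appendix 4 code 9.1 (AIA sample not collected) is an important deviation coded as having no effect on immunogenicity, so PPS drops those subjects and PPS2 keeps them. SS-Completers imputes nothing but requires treatment until Week 26, so it leaves the treatment-policy estimand. HbA1c has a two-way tipping-point analysis (SAP 11.7.1.3); AIA has none. SAP 3.1 records no removal of the worst-case analysis.

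**The case against.** **The size rests on assumptions.** SAP 5.1 reports discontinuation, not missing samples, and return visits, wide windows and use of post-discontinuation data all reduce the gap. This stands. A reader might infer from the reported discontinuation that the error was badly inflated in this trial; the documents do not support that. At 5% missing, shrinkage alone gives 6.6–7.0% at Lantus 20–30%.

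**The rule is in the protocol.** It is not a SAP departure, and preferring another primary imputation is a matter of design. This stands too, and is why replacing the rule is not demanded here.

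**Unadjusted has a natural meaning.** A reader might call the word meaningless in a model without covariates. It most naturally means the crude Lantus proportion: the SAP cites a method paper on covariate-adjusted differences, and its ERIPD analysis adds a factor to the model. The link to π_2 even favours the reading that counts imputed positives. But no sentence says so, and the wording about the actual observed rate leaves the other reading open.

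**The imputation is examined.** SS-Completers avoids it, PPS may remove much of it, and the promised composite analysis is present. It would therefore be too strong to say that nothing addresses the imputation. What is absent is an analysis identified as the promised worst case, or any that treats missing subjects differently by arm. Missing counted positive in both arms cannot fill that role, since it is already the primary rule.

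**Always biased toward equivalence?** No. That follows only for similar missingness. With unequal missingness the bias at each margin can go either way.

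**Conclusion.** The concern holds in this form. If missingness is similar in the arms, the missing-as-event rule shrinks the true difference by (1−f) and makes the primary test anti-conservative, with errors as tabulated above under assumed equal missingness. The excess need not appear at both margins: at Lantus 20%, 5% missing and the complete-subject margin, the lower error is 4.6%. The rate that selects the margin is not settled by the text, and the choice changes the upper error at 20% missing from 14.9% to 19.8% (Lantus 30%). The promised worst-case imputation is not listed.

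A reader might infer that taking imputed positives out of the margin rate restores a 5% test. It does not: the shrinkage remains, and above a 50% Lantus rate that step raises the error.

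**What to change.** 1. Add to SAP 11.6.1.3 a two-way tipping-point analysis for AIA that varies the share of missing subjects counted positive from 0 to 100% separately in each arm. Name it as the worst-case analysis of Protocol 12.7.1 and fix the plausible region before unblinding. A grid is better than the opposite-arm extreme alone: with missing positive on test and negative on Lantus, truly equal products pass only 47/7% (Lantus 20%) or 55/13% (Lantus 30%) of the time at 5/10% missing.
2. State in SAP 5.1 and 11.6.1.1 that the Table 3 margin is read once from the Lantus rate without imputed positives, in Lantus subjects of the Safety Analysis Set with both Week 12 and Week 26 results, and is used for the primary and all sensitivity analyses. Subjects positive at Week 12 but missing Week 26 stay out of this rate; keeping incomplete positives without incomplete negatives would raise it. This lowers the error below a 50% Lantus rate and raises it above.
3. State that Table 4 leaves error above 5% when samples are missing, and that with this margin power falls below the stated 83–85% at lower Lantus rates but not above 50%, with the figures from step 7.
4. Record these changes in SAP 3.1 before the blinded team is unblinded.

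The cost is SAP text and programming, plus the power loss at lower Lantus rates. Items 1 to 3 expose and limit the inflation without removing it. Arm-specific multiple imputation that keeps observed positives as events can be added as a sensitivity analysis. Making it primary is a judgement for the sponsor, since replacing a protocol-fixed rule after follow-up in an open-label trial carries its own risk.
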